4. JUSTIFICATION AND OBJECTIVE OF THE CLINICAL TRIAL

FMT for ADP is a promising approach, given the documented role of bacteria in the pathogenesis of this condition. However, whereas a single FMT in patients with C. difficile colitis seems to be sufficient to achieve a high therapeutic success rate, an intensified therapy with daily or repeated FMT to firmly establish the donor microbiome in the recipient appears to be the therapy of choice in patients with chronic intestinal inflammation (as outlined above). However, repeated endoscopic FMT is costly and not feasible. An alternative therapeutic modality is the repeated application of FMT via enemas. But this approach is suboptimal due a) patient preferences (oral> rectal), b) the occurrence of severe rectal pain during the application in patients with concomitant cuffitis and c) problems with retention of the enema content.⁵⁸⁻⁶⁰ Thus the optimal approach is a combination of endoscopic FMT and consecutive therapy with oral FMT to help establish the donor microbiome in the host. With the recent availability of capsulated FMT this approach became feasible. The objective of this proof of concept trial is to evaluate the safety of endoscopic followed by oral FMT in patients with ADP and to estimate the effect size to be achieved from FMT therapy in patients with ADP for subsequent evaluation in a large definitive trial. A secondary objective is to study the microbial engraftment of donor FMT in the recipients.

Specific hypothesis

We hypothesize that FMT is a novel therapeutic option for patients ADP. This form of pouchitis is predestined to benefit from FMT, since bacterial dysbiosis, which can only be controlled with antibiotics, appears to be the major driver of the clinical symptoms. We choose two distinct outcomes, a clinical and translational aim, to investigate the effect of FMT in patients with ADP.

Aim 1: Evaluation of safety, tolerability and clinical effectiveness (measured as clinical response or remission and discontinuation of antibiotic therapy) of FMT in patients with ADP.

Aim 2: Evaluation of the impact of FMT on the fecal bacterial microbiome in patients with ADP, which will provide functional data about possible mechanisms of this therapy.

• Safety profile of fecal transplant

Fecal transplant has an excellent safety profile in patients with C. difficile colitis. Also FMT for C. difficile colitis seems to be safe in immunocompromised patients.

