5. TRIAL ENDPOINTS

• Primary Endpoint:

Safety and Tolerability of FMT

• Number of study patients, who discontinued therapy

- Adverse events grouped by body system
- Changes in laboratory values
- Secondary Endpoints
- Clinical remission (mPDAI score ≤ 4 points) and no need for antibiotic therapy at week 4.
- Clinical remission (clinical mPDAI score ≤ 4) and no need for antibiotics at week 8*.
- Clinical remission (clinical mPDAI score ≤ 4) and no need for antibiotics at week 16*.
- Endoscopic improvement of active pouchitis (decrease from baseline in mPDAI endoscopic subscore ≥ 2 points) at week 4.
- Response: Symptomatic improvement of active pouchitis (decrease from baseline in mPDAI clinical subscore ≥ 2 points) and no need for antibiotic therapy at week 4.
- Response: Symptomatic improvement of active pouchitis (decrease from baseline in mPDAI clinical subscore ≥ 2 points) and no need for antibiotic therapy at week 8*.
- Response: Symptomatic improvement of active pouchitis (decrease from baseline in mPDAI clinical subscore ≥ 2 points) and no need for antibiotic therapy at week 16*.

*Only patients who do not continue in open label extension

- Exploratory analyses (OL=Open label):
- Endoscopic improvement of active pouchitis (decrease from baseline in mPDAI endoscopic subscore ≥ 2 points) at in open label extension week 8.
- Clinical remission (mPDAI score ≤4 points and a decrease in the baseline mPDAI> 2 points) and no need for antibiotic therapy at week 10 OL.
- Clinical remission (clinical mPDAI score ≤ 4) and no need for antibiotics at week 14 OL.
- Clinical remission (clinical mPDAI score \leq 4) and no need for antibiotics at week 22 OL.
- Response: Symptomatic improvement of active pouchitis (decrease from baseline in mPDAI clinical subscore ≥ 2 points) and no need for antibiotic therapy at week 10 OL.
- Response: Symptomatic improvement of active pouchitis (decrease from baseline in mPDAI clinical subscore ≥ 2 points) and no need for antibiotic therapy at week 14 OL.
- Response: Symptomatic improvement of active pouchitis (decrease from baseline in mPDAI clinical subscore ≥ 2 points) and no need for antibiotic therapy at week 22 OL.
- Symptomatic worsening of active pouchitis (decrease from baseline in mPDAI clinical subscore ≥ 2 points) from FMT week 0 week 16
- Quantitative changes in mPDAI from baseline values
- Quantitative changes of calprotectin from baseline
- Alterations in stool microbiome after FMT

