The rectal bleeding frequency will be calculated for the three evaluation days. The relative frequency for rectal bleeding will be calculated based on the total number of stools passed over the same three evaluation days ((total #stools with blood/total #stools)*100). The relative frequency will be evaluated against the following categories:

0% (none) < 20% (rare) > 20% (present daily)

Please note that the words, "none", "rare", and "present daily" in parentheses, correspond to the rectal bleeding categories on the mPDAI. These categories will be used to assign a mPDAI score for rectal bleeding.

Fecal urgency/abdominal cramping

The fecal urgency/abdominal cramping frequency will be calculated for the three evaluation days. The relative frequency for fecal urgency/abdominal cramping will be calculated based on the total number of stools for the same three evaluation days ((total #stools with cramping or urgency/total #stools)*100). The relative frequency will be evaluated against the following categories:

0% (none) < 50% (occasional) > 50% (frequent)

As with rectal bleeding, the words, "none", "occasional", and "frequent" in parentheses, correspond to the fecal urgency/abdominal cramping categories on the mPDAI. These categories will be used to assign a mPDAI score for fecal urgency/abdominal cramping.

Fever

If a subject indicates that they had a fever on none of the three evaluation days, the mPDAI score for "absent" will be recorded. If a subject indicates that they had a fever on one or more of the three evaluation days, the mPDAI score for "present" will be recorded.

20. STATISTICAL ANALYSIS

The following endpoints will be assessed

• Primary Endpoint:

Safety and Tolerability of FMT

- Number of study patients, who discontinued therapy
- Adverse events grouped by body system
- Changes in laboratory values
- Secondary Endpoints Clinical remission (mPDAI score <4 points and a decrease in the baseline mPDAI > 2 points) and no need for antibiotic therapy at week 4.
- Clinical remission (clinical mPDAI score ≤ 4) and no need for antibiotics at week 8*.
- Clinical remission (clinical mPDAI score ≤ 4) and no need for antibiotics at week 16*.
- Endoscopic improvement of active pouchitis (decrease from baseline in mPDAI endoscopic subscore ≥ 2 points) at week 4.

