The primary endpoint is the evaluation of safety and tolerability of FMT in patients with ADP. Secondary endpoints are endoscopic and clinical remission at week 4 in conjunction with no need for antibiotic therapy, clinical response and remission and no need for antibiotics at week 4,8 and 16, endoscopic improvement of pouchitis and quantitative changes of calprotectin after the initial FMT. All subjects with missing data for determination of endpoint status will be considered as a non-responder in the intention-to-treat analysis. For dichotomous outcomes we will compute the percentage of subjects having the event along with a 95% confidence interval. For continuous outcomes we will compute the mean and a 95% confidence interval for the mean as well as descriptive statistics such as median, range and upper and lower quartiles. In addition to computing these measures for all 20 subjects, we will compute them for subgroups of interest (e.g. endoscopic active vs inactive ADP). These estimates can then be used in the planning of a larger, hypothesis-based study.

• Sample size calculation

This trial is designed as a proof-of-concept study of FMT therapy, not a definitive evaluation of FMT therapy in patients with ADP. The goal is to evaluate the safety and feasibility of such a trial, as well as to estimate the effect sizes in placebo and FMT therapy groups in order to accurately estimate the sample size needed for subsequent evaluation in a larger definitive trial. Nonetheless, we estimated the minimum effect size this pilot study can detect. We assume a placebo remission rate (defined as clinical remission and no need for antibiotics) of 10%. The low placebo response rate is based on the inclusion criterion, which selects only patients needing continuous or recurrent antibiotic therapy in the setting of ADP. With a follow-up of 16 weeks with the requirement of clinical remission without antibiotic therapy at end of follow-up, a placebo response rate beyond 10% is highly unlikely. The recent case series of Stallmach et al. suggests an antibiotic-free remission rate of 80% and a response rate of 100% in the setting of repeated FMT.⁴⁹ With 20 patients (1:1 randomization), and a placebo response rate of 10%, we will have 80% power to detect an effect difference of 67.5%, that is, an antibiotic-free remission rate

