of 77.5% in the treatment group (2-sided, alpha=0.05, Fisher-Irwin's exact conditional test). Thus, even with this small proof-of-concept design, we could observe a significant effect in the range of effect size reported in recent case series.

Microbiome Analyses

From each patient 1 stool sample will be collected before transplant and twice after the transplant (week 3 and 4). Patients in remission will collect 2 more stool samples in week 8 and 16. Patients in the open label extension trial will collect stool samples after transplant in week 8, 10, 14 and 22. Assuming that 9 patients enter remission in the placebo controlled phase (9x4= 36 samples) and 11 patients enter the open label extension (11x7=77 samples) a total of 116 samples will be analysed. All microbiome analyses will be conducted by OpenBiome, which will donate time and materials for the analyses. The gut microbiome of donors and patients will be analysed through deep sequencing of the 16S ribosomal RNA gene amplified from stool samples. Microbial engraftment will be operationalized through the donor similarity index (DSI) used to evaluate the degree of engraftment in FMT recipients over time (after 2,4,8 and16 weeks).⁶¹ We will measure DSI over time to elucidate the stability of engraftment and its relationship to clinical observations. In addition to 16S rRNA sequencing, we will save aliquots of stool for metabolomic characterization. In particular, given the potential role of butyrate in ameliorating inflammation, we're especially interested in measuring short chain fatty acid levels in stool before and after FMT. We plan to collect stool samples for characterization at baseline and at 2, 4, 8 and 16 week intervals after treatment.

21. STUDY VISITS CHART

1.1 STUDY VISITS CHART PLACEBO CONTROLLED TRIAL SCREENING – WEEK 4 (SITE VISIT)

Visit	Screening	1	2	3	4	5	Early termination ^g
Type of visit	Site	Site	Phone	Site	Phone	Site	Phone/site
Derr	-14	0	7	15	26	28	
Day	-14	0	+/-1	+3	+/-1	+/-3	
Week	-2	0	1	2	4	4	
Medical History	Х						
mPDAI score		Х	Xd	X ^d	X ^{g(!)}	Х	X
Concomitant Medication	Х	Х	X	X	X	Х	X
Adverse Events		Х	X	Х	Х	Х	X
Physical Exam	Х					Х	Х
Blood Tests	Х					Х	Х
Pregnancy Test (urine)	Х	Х					
Test FMT capsule	Х						
Dispense FMT capsules		Х					
10-14 day antibiotic therapy pre- transplant	Х				Xc	Xc	Xc
Stool sample	Xe			X ^f	X ^f	X ^g	Х
Sigmoidoscopy (Pouchoscopy		Х				Xa	
Endoscopic FMT		Х					
Distribute/Review Subject Diaries ^b	Х	Х	Х	Х	Х	Х	Х

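### The clinical analysis paragraph plans estimates for all 20 subjects and does not carry over the FMT-versus-placebo estimates and Fisher test on which the objective and the power rest

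*Combined protocol and SAP*

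**What the plan says.** All references are to the combined protocol and SAP.

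- **Section 20, Clinical analyses.** Dichotomous outcomes get a percentage with a 95% confidence interval. Continuous outcomes get a mean with a 95% interval plus descriptive statistics. On whom: "In addition to computing these measures for all 20 subjects, we will compute them for subgroups of interest", with endoscopically active versus inactive disease as the one example. On use: "These estimates can then be used in the planning of a larger, hypothesis-based study". The paragraph opens with the primary endpoint, safety and tolerability, and mentions an intention-to-treat analysis in which missing endpoint status counts as non-response.
- **Section 4, objective.** Besides safety, the trial is "to estimate the effect size to be achieved from FMT therapy in patients with ADP for subsequent evaluation in a large definitive trial".
- **Section 20, Sample size calculation.** The goal is safety and feasibility, "as well as to estimate the effect sizes in placebo and FMT therapy groups". The power statement assumes 1:1 randomisation of 20 patients, 10% remission on placebo, and an antibiotic-free remission rate "of 77.5% in the treatment group (2-sided, alpha=0.05, Fisher-Irwin's exact conditional test"). The 10% is defended by the length of follow-up: "With a follow-up of 16 weeks with the requirement of clinical remission without antibiotic therapy at end of follow-up".
- **Week-4 remission.** Section 5 lists "Clinical remission (mPDAI score ≤ 4 points) and no need for antibiotic therapy at week 4". Section 20 adds a further condition: "decrease in the baseline mPDAI > 2 points) and no need for antibiotic therapy at week" 4. The table of contents repeats the Section 20 form; the summary in Section 1 matches Section 5.
- **Weeks 8 and 16.** Remission and response at these times are limited, in Sections 1, 5 and 20, to patients who do not continue into the open-label extension.
- **Section 1, Statistical analysis.** Intention-to-treat for remission and response, and Wilcoxon rank sum tests on pre- and post-treatment mPDAI.

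**The concern.** This is a 1:1 randomised, double-blind, placebo-controlled pilot whose stated product is an effect size for a larger trial. The one paragraph that says what will be computed describes a single-group analysis. Followed as written, its headline result is a rate averaged over FMT and placebo patients, and that rate is offered for planning the next study.

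The primary endpoint is affected too. A summary of adverse events, discontinuations and laboratory changes over all 20 subjects in the randomised phase mixes placebo patients into an estimate meant to describe FMT. The only report said to be broken down by treatment group is the six-monthly one for the DSMB (Section 18), which is monitoring and not the final analysis.

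Leaving the comparison out of the analysis text also leaves its details open: which time point, which remission definition, which interval, and how patients who move to open-label FMT are counted. In a trial of this size each of these can change the result, and none should be settled after unblinding.

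**Working it through.** **Inputs.** N = 20, 1:1, so 10 per arm; placebo 10%; FMT 77.5%; two-sided alpha 0.05; Fisher exact test; stated power 80% (all Section 20, Sample size calculation). Nine remitters in the placebo-controlled phase (Section 20, Microbiome Analyses).

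**1. The plan's own power figure.** Let a and b be the numbers in remission on FMT and placebo. Power is the sum of Bin(a; 10, 0.775) × Bin(b; 10, 0.10) over all of the 11 × 11 tables with two-sided Fisher p ≤ 0.05. The result is 0.8016. The stated 80% is correct, and it is the power of a between-arm test. Against 1/10 on placebo, the smallest significant FMT result is 7/10 (p = 0.0198).

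**2. What the pooled rate estimates.** (0.10 + 0.775)/2 = 0.4375, or 8.75 of 20. It is not 10%, not 77.5%, and not the difference of 67.5 points.

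**3. What a pooled count leaves open.** Take the plan's own 9 remitters. 9/20 = 45%, exact 95% CI 23% to 68%, whatever the split:

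| FMT vs placebo | Difference (points) | Newcombe 95% CI | Fisher p |
|---|---|---|---|
| 8/10 vs 1/10 | 70 | 27 to 87 | 0.0055 |
| 7/10 vs 2/10 | 50 | 7 to 74 | 0.070 |
| 6/10 vs 3/10 | 30 | −12 to 60 | 0.37 |
| 5/10 vs 4/10 | 10 | −29 to 45 | 1.0 |

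For the first row, p = 2 × (45 × 10 + 10 × 1)/167,960 = 0.0055. In the second row the interval excludes zero while the test does not reject. The interval method and the deciding test therefore have to be named in advance.

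**4. Safety.** With no events among n patients, the upper limit of the exact two-sided 95% interval is 1 − 0.025^(1/n):

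- n = 20 (all subjects): 16.8%.
- n = 10 (FMT arm of the randomised phase): 30.8%.
- n = 19: 17.6%. This is everyone ever exposed to FMT if the 10 × 0.90 = 9 placebo patients expected not to remit all accept open-label FMT (an assumption).

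These are two different questions, and the pooled randomised-phase figure answers neither.

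**5. Time point.** The 10% placebo rate is argued from week 16, but the week-16 endpoint excludes patients who enter the extension, which is offered to those not in remission at week 4 or with a flare. As an illustration, apply the design rates at week 4 and let every non-remitter enter. The week-16 set would then hold on average 10 × 0.775 = 7.75 FMT patients and 10 × 0.10 = 1 placebo patient. The chance of no placebo patient at all is 0.9^10 = 0.35. The powered test needs all 10 per arm. The non-responder rule does not settle this, because it covers only missing data.

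**6. Week-4 definition.** Sections 1 and 5 require a score threshold and no antibiotics; Section 20 and the table of contents also require a fall of more than 2 points. The clause can change who counts. Baseline uses the three days before week 0 (Section 19), when patients are on antibiotics until 24 hours before FMT (Section 7). The score cannot go below 0, so a patient with a baseline of 2 or less can never meet the clause.

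**The case against.** The strongest reply is that a by-arm analysis is plainly intended. The next subsection gives effect sizes in the two groups as the goal and names the test, its sidedness and alpha. Intention-to-treat in a randomised trial ordinarily means comparison by assigned arm. The subgroup list is introduced only as an example, so arm is not excluded. Arm is recorded for every patient, so nothing is lost for good. All of this stands. A reader might infer that the plan rules out a comparison or would report only pooled results; the documents do not support that. What remains is that a goal and a power assumption do not specify an analysis, and the paragraph that should specify it does not.

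Three other stronger readings also fail.

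- A reader might infer that Section 20 sets a stricter week-4 threshold, below 4 instead of 4 or less. The table of contents gives the same heading with ≤ 4, and the open-label definition in Section 20 also has ≤ 4. The strict sign is very likely a text-conversion artefact. The real discrepancy is the clause on the fall of more than 2 points.
- A reader might infer that pooling makes FMT look about twice as well studied as it is (16.8% against 30.8%). That contrast holds for the randomised phase only. Counting open-label exposure, the limit could be close to the pooled figure (17.6% under the assumption above).
- A reader might infer from Section 1 that paired data will be analysed with an unpaired test. The rank sum test may instead be meant for change compared between arms. This is a matter of wording.

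It can also be said that this is only a pilot. Its stated purpose is to estimate arm-specific effects, so that argues for specifying them.

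**Conclusion.** The point holds as a specification gap in one paragraph and should be fixed before unblinding. The power figure is right (80.2% against 80%) and the sample size needs no change. The stated main summary would give about 43.75% at the design rates, which cannot serve the planning purpose that the paragraph assigns to it. It would also blend placebo patients into the randomised-phase safety estimate.

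Two linked items must be settled before the Fisher test can be run as powered: the time point of the remission endpoint, and whether week-4 remission includes the clause on the fall of more than 2 points.

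The 43.75% rests on the plan's own rates. The splits of 9/20 are illustrations built on the plan's assumed 9 remitters. The exposed-patient safety figure assumes that every expected placebo non-remitter accepts open-label FMT, and the week-16 illustration assumes that the design rates apply at week 4 and that all non-remitters enter the extension.

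**What to change.** In Section 20, Clinical analyses, replace the all-subjects summary as the main analysis with wording such as:

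> Efficacy and safety outcomes of the placebo-controlled phase will be reported by randomised arm: rate with exact 95% CI, or mean with 95% CI, per arm. For remission, the FMT minus placebo difference will be given with a 95% CI by [named method], and the two-sided Fisher exact test is the test of record. Safety after open-label FMT will be reported separately, and also for all patients ever exposed to FMT. The summary for all 20 subjects is supplementary.

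Then:

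- State one time point for the tested remission endpoint. If it is week 16, count extension entrants by a stated rule (for example as non-responders) and do not exclude them.
- Reconcile the week-4 definitions in Sections 1 and 5 with Section 20 on the clause about the fall of more than 2 points.
- Minor: in Section 1, say that the rank sum test compares change from baseline between arms, and use a signed-rank test for any within-patient comparison before and after treatment.

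The cost is SAP wording and a few more tables, with no new data and no change in sample size or power. By-arm intervals will be wide (8/10 runs from 44% to 97%; 1/10 from 0.3% to 45%), which is the real precision of 10 patients per arm.

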 - Active pouchitis, defined as a mPDAI \geq 5 and a history of \geq 4 antibiotic therapies for pouchitis in the last 12 months

or

Need for ongoing antibiotic therapy (> 4 weeks) to maintain clinical remission and a history of at least 2 attempts in the last 24 months to stop antibiotic therapy resulting in pouchitis episodes. Concomitant oral 5 ASA or local therapies containing 5-ASA (enemas, suppositories) or steroid enemas are permitted but not required but have to be stable for 4 (oral) or 2 weeks (topical) before inclusion in the study.

- Exclusion criteria
- Treatment with biologics (e.g. infliximab, adalimumab, golimumab, vedolizumab)
- Treatment with immunomodulators (azathioprine, 6-MP, methotrexate), steroids or any investigational drugs
- Use of cholestyramine
- Crohn's disease of the pouch
- Known cytomegalovirus infection of the pouch
- Clostridium difficile infection
- Isolated moderate or severe cuffitis
- Clinical significant strictures of the pouch inlet or outlet
- Concurrent intestinal obstruction
- History of familial adenomatous polyposis
- History of uncontrolled lactose intolerance
- History of confirmed (serological test and/or histology) celiac disease
- Pregnancy, breast feeding, or planning to become pregnant during the trial
- Non steroidal inflammatory medications (NSAIDs) as long-term treatment, defined as use for at least 4 days a week each month
- Dysphagia (oropharyngeal, esophageal, functional, neuromuscular)
- History of recurrent aspiration episodes
- Proven gastroparesis
- Allergy to the following generally regarded as safe ingredients (GRAS): glycerol, acid resistant HPMC, gellan gum, cocoa butter, titanium dioxide
- Adverse event attributable to previous FMT
- Allergy/intolerance to pump inhibitor therapy
- Any condition for which the investigator thinks the FMT treatment may pose a health risk (e.g. severely immunocompromised)
- Participation in another clinical trial within the last 30 days, simultaneous participation in another clinical trial, or previous participation in this trial
- During the trial period until one week after the trial end: Non-use of appropriate contraceptives in females of childbearing potential (e.g. condoms, intrauterine device {IUD}, hormonal contraception, or other means considered adequate by the responsible investigator) or in males with a child-fathering potential (condoms, or other means considered adequate by the responsible investigator during treatment

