If the patient is not willing to continue in the open label part of the study, he/she will be followed in the regular arm with visits 6-9.

Study visits for patients at remission at phone visit 4 and site visit 5

Phone visit 6 will evaluate for adverse events and review the adverse event diary. At this point (4 weeks after stopping the oral FMT) the patient can stop filling out the daily adverse event diary. However, the patient will be reminded to bring the completed adverse event diary to site visit 7. Additionally, the mPDAI will be calculated and the concomitant medications will be assessed.

Site visit 7 will collect all pages of the adverse event diary, and review the adverse events, which occurred since visit 6. A physical exam and blood tests will be performed and the mPDAI will be calculated. The concomitant medications will be assessed. A stool sample will be collected from the patient.

Site visit 8 will review new adverse events, concomitant medications and the mPDAI score. A stool sample will be collected from the patient.

On the last phone visit 9 the coordinator will review serious adverse events only, which may have occurred since visit 8.

Open label extension period

After at least 10 days of antibiotic therapy a pouchoscopy and FMT will be performed at site visit 6OL. A physical exam will be completed, adverse events and concomitant medications reviewed. Female patients will provide a urine sample for a pregnancy test before FMT. Similar to the previous FMT the study patient will be started on omeprazole 20 mg (1 tablet/daily) as long as he/she undergoes oral FMT therapy.

In phone visit 7OL the coordinator will ask the study patient if adverse events occurred, review the adverse event diary, and will evaluate the clinical components of the mPDAI of the last 3 days before the phone call (stool frequency, rectal bleeding, fecal urgency/ abdominal cramping, fever) as well as the concomitant medications.

At site visit 8OL the study coordinator will ask the study patient if adverse events occurred, review the adverse event diary, and will evaluate the clinical components of the mPDAI of the last 3 days before the visit (stool frequency, rectal bleeding, fecal urgency/ abdominal cramping, fever) as well as review the concomitant medications. The coordinator will collect the stool sample from the patient, which should be collected 1-3 days after the end of the oral FMT therapy .

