The 9OL site visit will review adverse events and the adverse event diary, collect safety blood labs, perform a physical exam and calculate the mPDAI. A stool sample for the stool bank will be collected from the patient. A pouchoscopy will also be performed.

Phone visit 10OL will evaluate for adverse events and review the adverse event diary. At this point 4 weeks after stopping the oral FMT the patient can stop filling out the daily adverse event diary The patient will be reminded to bring the filled out adverse event diary to site visit 11OL. Additionally, mPDAI will be calculated and the concomitant medications will be assessed.

Site visit 110Lwill collect all pages of the adverse event diary, and review the adverse events, which occurred since visit 100L. A physical exam and blood tests will be performed and the mPDAI will be calculated. The concomitant medications will be reviewed. A stool sample for the stool bank will be collected from the patient.

Site visit 12OL will review new adverse events, concomitant medications and the mPDAI score. A stool sample for the stool bank will be collected from the patient.

On the last phone visit 13OL the coordinator will review serious adverse events only, which may have occurred since visit 12OL.

Study patients experiencing a recurrence of symptoms in the open label extension period

If the study patient is experiencing worsening of disease after the second FMT, antibiotic therapy will be re-initiated as a standard of care approach. The patient will nevertheless be followed up according to the same schedule as patients not experiencing a relapse.

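### The remission and response endpoints after week 4 set no look-back period and no rule for interim antibiotics, so a patient who relapsed and was retreated can be counted as an antibiotic-free success

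*Combined protocol and SAP*

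**What the plan says.** Sections 5 and 20 word each remission and response endpoint at a named week. The week 16 remission endpoint, for example, ends "and no need for antibiotics at week 16". The week 8 and week 16 endpoints are limited to patients who do not continue in the open-label extension. The sample size paragraph in Section 20 supports its placebo rate with the same time-point condition: "With a follow-up of 16 weeks with the requirement of clinical remission without antibiotic therapy at end of follow-up".

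Two passages in Section 7 keep retreated patients under observation:

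- After a recurrence in the extension, antibiotics are restarted. Then: "The patient will nevertheless be followed up according to the same schedule as patients not experiencing a relapse".
- A patient who flares between days 1 and 28, restarts antibiotics and declines the extension stays in the trial: "he/she will be followed in the regular arm with visits 6-9". A patient not in remission at phone visit 4 who declines is likewise followed as remitters are.

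The clinical score uses the last three diary days (Section 19; note b to the visit charts in Section 21). The only failure rule in Section 20 concerns missing data: such patients are non-responders. No section defines what no need for antibiotics means over time.

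**The concern.** Aim 1 in Section 4 measures effectiveness partly by stopping antibiotics. If a remission produced by a rescue course can be scored as antibiotic-free, the late endpoints no longer isolate what FMT did. The problem is not confined to FMT recipients: a rescued placebo patient who declines the extension belongs to the week 8 and week 16 set.

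Two features make the gap matter. First, one of the two qualifying subtypes in Section 6 is episodic, defined by active disease plus a history of at least 4 "antibiotic therapies for pouchitis in the last 12 months". Spells of being well and off antibiotics between courses are part of that history. Second, Section 20 wants these estimates for planning a larger trial, and defends a 10% placebo rate by the antibiotic-free requirement itself. If that requirement looks only at the visit, the defence is weaker than it appears.

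**Working it through.** **1. The plan's own figure.** Inputs from Section 20: 20 patients randomised 1:1, so 10 per arm; placebo rate 10%; FMT rate 77.5%; two-sided alpha 0.05; Fisher's exact conditional test. Summing the two binomial distributions over every table with p ≤ 0.05 gives power 80.2%, against the stated 80%. The figure reproduces, and this point alleges no arithmetic error.

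**2. Can the score screen out retreated patients?** In Appendix C the clinical items have maxima of 2 (frequency), 1 (bleeding), 2 (urgency or cramps) and 1 (fever): 2 + 1 + 2 + 1 = 6. The remission threshold at weeks 8, 16, 14 OL and 22 OL is a clinical score of at most 4, which excludes only scores of 5 and 6. The antibiotic component therefore does much of the work, and it is the undefined part.

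**3. Does the timing allow it?** The length of a rescue course is not stated. As an assumption, take the 10 to 14 days of the pre-transplant course (Section 21 chart). Adding three scored days, a course must start 13 to 17 days before the visit to be over before scoring begins.

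| Interval | Nominal | Shortest under the visit windows |
|---|---|---|
| Day 28 flare to week 8 visit (day 56 ± 5) | 28 days | 51 − 28 = 23 days |
| Week 8 to week 16 visit (day 112 ± 7) | 56 days | 105 − 61 = 44 days |
| Visit 9OL (day 28 ± 3) to 11OL (day 56 ± 5) | 28 days | 51 − 31 = 20 days |
| Visit 11OL to 12OL (day 112 ± 5 in Section 10, ± 7 in the chart) | 56 days | 107 − 61 = 46, or 105 − 61 = 44 days |

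Every interval exceeds 17 days, so the sequence fits. This shows that it is possible, not that it is frequent.

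**4. Does any rule catch it?** A retreated patient who attends has complete data, so the missing-data rule does not apply. Where the plan wants an interval it writes one: symptomatic worsening is assessed from week 0 to week 16.

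**5. Weight of one patient.** 1/11 = 9.1 points among the 11 patients Section 20 expects in the extension; 1/10 = 10 points in a full arm; 1/9 = 11.1 points if the week 8 and week 16 set is the 9 patients expected in remission.

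**6. Illustration only.** Suppose a fraction f of true failures, equal in both arms, is retreated and then scored as remission. Observed rates become 0.10 + 0.90f and 0.775 + 0.225f, so the difference is 0.675(1 − f). Exact power with 10 per arm:

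| f | Placebo | FMT | Difference (points) | Power |
|---|---|---|---|---|
| 0% | 10.0% | 77.5% | 67.5 | 80.2% |
| 5% | 14.5% | 78.6% | 64.1 | 72.6% |
| 10% | 19.0% | 79.8% | 60.8 | 65.2% |
| 20% | 28.0% | 82.0% | 54.0 | 51.0% |
| 30% | 37.0% | 84.3% | 47.3 | 38.6% |

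The documents give no value for f. The table also keeps 10 per arm, which the restriction at weeks 8 and 16 does not guarantee.

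**The case against.** A reader might infer that the plan judges antibiotic need only on the visit day and so does count retreated patients as FMT remissions. The documents do not support that. No passage says only, and the sample size clause is a rationale for the placebo rate, not an endpoint definition. Section 1 ties outcome to needing antibiotics to control symptoms, so a recorded rescue course could be read as need.

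Other text could also remove some of these patients. Section 6 does not permit antibiotics for pouchitis, Section 16 lists disease progression requiring other treatment as a possible reason for withdrawal, and the charts provide early termination between visits 6-8 and 6OL-12OL. Patients who leave that way would have missing data and count as non-responders. This stands as far as it goes, but none of it mentions rescue as an endpoint failure, and Section 7 expressly keeps the two groups above in follow-up.

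The randomised-phase route is narrow. It rests mainly on patients who decline the extension, and the planning split of 9 in remission plus 11 in the extension equals 20, leaving no decliners. For a week 4 remitter who relapses later, Section 7 says nothing about follow-up after rescue. This also stands.

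A reader might also size the problem from days off antibiotics: with four two-week courses a year, 1 − 4 × 14/365 = 85% of days. That rests on an assumed course length, covers only the episodic subtype, and is a share of days, not a misclassification rate.

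Finally, remission at a visit and sustained antibiotic-free remission are both legitimate targets. True, but the plan must say which it estimates, and Aim 1 and the 10% rationale point to the sustained one.

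**Conclusion.** The concern holds as a gap in definition with a real path to misclassification, not as demonstrated misclassification. The path is explicit for weeks 14 and 22 OL, possible but tighter for week 10 OL, and narrower for weeks 8 and 16, where both arms are exposed. Its frequency is unknown. One patient is worth about 9 points in the extension and about 10 in an arm of 10, more if the week 8 and week 16 set is smaller. Dilution of the arm difference is plausible, but follows only under an assumed f. The safety primary endpoint is unaffected and week 4 remission lies outside this point. The change should be made because the late estimates are intended to inform the next trial.

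**What to change.** In Sections 5 and 20, for analysis only:

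- Define the antibiotic component of every remission and response endpoint after week 4 as no antibiotic course for pouchitis at any time from the relevant FMT to the assessment. The clock starts at week 0 or, for the extension, at visit 6OL, so the pre-FMT course is excluded.
- Count a patient retreated in that interval as a non-remitter and non-responder from that date on.
- Report the visit-day version as descriptive.

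The cost is small. Concomitant medication is already reviewed through week 16 or week 22 OL; the form should hold start and stop dates and indication, which the visit lists do not spell out. Late remission and response rates will be somewhat lower. The stated power inputs do not change, and neither does clinical management.
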